2.0 Objectives

The overall objective of this study is to use mixed methods to assess the feasibility and acceptability of delivery of HIV injectable medications outside of the traditional HIV clinic setting and within community-based settings serving individuals at high risk of not engaging in care. Specifically, we propose to examine a set of implementation questions and effectiveness/clinical questions as identified in Section 1.2 above.

Protocol Title: **CAB-RPV LA Implementation Strategies for High-Risk Populations**

3.0 Study Design

The study design for the overall study is a hybrid implementation-effectiveness study. We will use both qualitative and quantitative methods to conduct our work. Objective 2, the focus of the current protocol, will be a three-arm cohort study that uses quantitative methods. Our learning from this objective will be supplemented with qualitative data in Objective 3. In this study, we test our primary implementation strategy, changing the service delivery site to a community-based clinical intervention, while observing and gathering information on relevant clinical outcomes and community organization and clinical provider experiences.

Our overall analytic approach will include collecting qualitative data from potential patients, health care providers and community organizations related to feasibility and satisfaction with the model in Objectives 1 and 3; and quantitative Electronic Health Record (EHR) and participant survey data to address Objective 2 outcomes. Objective 1 has already been completed and included formative, pre-implementation work, specifically qualitative interviews, to assess intervention acceptability, feasibility, and appropriateness from the patient perspective that will help us define the final implementation blueprint for implementing the Objective 2 intervention. Objective 2 will be a cohort study comparing three groups: individuals who receive CAB-RPV LA at Project Trust, individuals who receive CAB-RPV LA in the HIV clinic, and individuals who share characteristics of Cohort 1 and are engaged in standard of care. Objective 3 will use qualitative methods to examine the in-depth experiences of patients who received CAB-RPV at the community site about their experiences and satisfaction with the model; and with health care providers and other individuals working in the community organizations regarding their experiences with the new service delivery model and plans for sustainability related to CAB-RPV LA treatment within their setting. Objective 1 was already approved by the BUMC IRB (protocol # H-40900; a protocol was not required by ViiV Healthcare for Objective 1 or Objective 3) and has been completed; **this protocol focuses on Objective 2 only.**

4.0 Potential Risks & Benefits

4.1 Potential Risks

The primary risk related to participation in the study is dropping out of care and not being linked to care. However, it is important to note that this is an ongoing risk for these patients in general given their social determinants of health putting them at higher risk of not being engaged in their care. There are risks related to the medication itself, which include injection site reactions, pyrexia, fatigue, headache, musculoskeletal pain, nausea, sleep disorders, dizziness, rash, diarrhea, pain/discomfort, nodules, induration, swelling, erythema, pruritus, bruising/discoloration, warmth and hematoma. Less common risks include gastrointestinal disorders, hepatobiliary disorders, weight increase, psychiatric disorders including anxiety (irritability, depression, abnormal dreams) and skin hypersensitivity. There is also the risk that if a participant is non-adherent to the injections, they may become resistant to cabotegravir and rilpivirine.

Special attention will be given to any medical issues related to the injections, including perceived soreness, fatigue, and other unintended consequences throughout the trial and standard referral to BMC will be made in such cases. It is important to note that CAB-RPV LA has been fully approved for use; the question for this study is NOT the effectiveness of the medication, but rather whether it can be delivered in non-traditional settings. Consent procedures will include detailed discussion of what the use of CAB-RPV LA will entail, both advantages and disadvantages, and an opportunity for the potential participant to ask questions. Once consent for screening has been provided,

Protocol Title: **CAB-RPV LA Implementation Strategies for High-Risk Populations**

study staff will confirm eligibility via EHR and conduct necessary testing (viral load, genotype). Study staff will contact potential participants within two weeks (once test results are received) and tell them if they are eligible for enrollment. If they are eligible, study staff will ask them to return for final study enrollment. All clinical data to determine eligibility will be collected from the EHR. There are also potential risks with the oral lead-in medications. Side effects of Vocabria include Headache, Nausea, Abnormal dreams, Anxiety, Insomnia. Side effects of Rilpivirine include Depressive disorders, Abnormal dreams, Rash, Abdominal Pain, Drowsiness, Dizziness, Vomiting, Nausea, Headache, Difficulty falling asleep or staying asleep. If participants choose to take the oral lead-in, they will be monitored throughout the oral lead in period for these side effects.

As with any study, there is the risk of loss of confidentiality as study personnel will have to access EHR data for individuals enrolled. However, we will ensure to take all precautions normally taken with use of EHR data in our institution, including only obtaining the data necessary to conduct the study. While study staff will need access to EHR data for purposes of ensuring eligibility, outcomes data will be obtained from the BMC Clinical Data Warehouse, which will be provided to the study team under strict protocols and will include study identifiers rather than names.

4.2 Potential Benefits

With new treatment advances, HIV is now a chronic disease that can be managed as long as PLWH remain adherent to ART. Yet, adherence is challenging for many individuals. Increased adherence to ART is a potential benefit for individuals, as are improved health outcomes as a result of greater adherence. It is hoped that providing treatment in alternative settings and via monthly injection rather than requiring adherence to daily pills will enable better adherence. This study can benefit other patients desiring alternative models and other institutions attempting to better keep higher risk persons adherent to care.

5.0 Study Subject Selection

5.1 Subject Inclusion Criteria

Cohort 1: Age \geq 18 years, English or Spanish speaking, HIV-positive, labs indicate that they are a candidate for the medication and virally suppressed, meaning that their HIV-1 ribonucleic acid is less than 50 copies per mL. Individuals enrolled in Cohort 1 must be willing to complete the locator form (Appendix G) in order to receive appointment reminders prior to their monthly/bi-monthly injection and ongoing follow-up by outreach and study staff to maximize potential for adherence.

Cohort 2: Currently enrolled in care at CID and receiving CAB-RPV LA injection, age \geq 18 years, English or Spanish speaking. Individuals enrolled must be willing to complete the locator form in order to receive appointment reminders prior to follow-up data collection.

Cohort 3: Enrolled in care at CID but not receiving CAB-RPV LA, age \geq 18 years, matched to participants demographically and in terms of other characteristics in Cohort 1 at a 1:1 ratio. Individuals in Cohort 3 will be receiving the Standard Care for HIV treatment in CID. Standard of care for this group includes access to regular appointments with their HIV provider, oral ART, case management services, etc. Individuals enrolled must be willing to complete the locator form in order to receive appointment reminders prior to follow-up data collection.

Our goal for all three cohorts is to enroll a percentage of women that is equivalent to the number of female patients served by the sites, approximately 20-30% female. Similarly, we will ensure that our sample includes individuals of color proportional to their representation within the setting across all three cohorts.

5.2 Subject Exclusion Criteria

Individuals who are not HIV positive, individuals under the age of 18 and individuals who do not speak English or Spanish will be excluded. Individuals who are not virally suppressed prior to beginning CAB will be excluded (excluding Cohort 3). Individuals who are not willing to take CAB-RPV LA after detailed discussion of what the use of CAB-RPV LA will entail, or are unable to undergo clinical eligibility testing to confirm eligibility will be excluded (excluding Cohort 3). If they have a history of integrase inhibitor mutations suggesting resistance to Cabotegravir or Cabenuva, a history or evidence of resistance to either INSTI or NNRTI, are currently pregnant or breastfeeding, or have HIV 1 with an HIV 2 co-infection or an HIV 2 infection, they will also be excluded. Individuals who have hepatic impairment at baseline lab draws will be excluded. Individuals who are on drugs that have known interactions with Cabenuva (including but not limited to carbamazepine, oxcarbazepine, phenobarbital, phenytoin, St Johns Wort, systemic Dexamethasone, rifabutin, rifampin and rifapentine) will be excluded. Individuals who have chronic Hepatitis B infection will also be excluded. If an individual is receiving CAB-RPV LA at CID, they are not eligible for Cohort 3.

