- If a potential participant is a BMC patient, study staff will obtain consent to move forward with the participant's care team in order to determine that the potential participant is eligible for the study.

All decisions will be made by study clinicians who will review medical documentation to determine that the potential participant meets eligibility criteria. Participants must be virally suppressed prior to enrollment, meaning that their HIV-1 ribonucleic acid measures less than 50 copies per mL. If a potential participant's EHR review indicates that they have a history of integrase inhibitor RT mutations suggesting resistance to Cabotegravir or Cabenuva, have demonstrated they have resistance to either an INSTI or an NNRTI, that the potential participant is currently pregnant, breastfeeding, or that the potential participant has HIV 1 with an HIV 2 co-infection or an HIV 2 infection, they will be deemed to be ineligible. Individuals who are not HIV positive, individuals under the age of 18 and individuals who do not speak English or Spanish are also ineligible. Individuals who are not virally suppressed are ineligible. Individuals who are not willing

Protocol Title: **CAB-RPV LA Implementation Strategies for High-Risk Populations**

to take CAB-RPV LA after detailed discussion of what the use of CAB-RPV LA will entail, or are unable to undergo clinical testing to confirm eligibility will be excluded. Individuals who are on drugs that have known interactions with Cabenuva, including but not limited to carbamazepine, oxcarbazepine, phenobarbital, phenytoin, St Johns Wort, systemic Dexamethasone, rifabutin, rifampin and rifapentine. Individuals who have chronic Hepatitis B infection will also be excluded. All women with child-bearing potential will have a pregnancy test conducted at a CLIA approved lab to rule out pregnancy.

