7.2 Cohorts 2 & 3 Recruitment, Screening & Enrollment

Cohort 2 Recruitment and Enrollment: Participants for Cohort 2 will be individuals who are receiving HIV in care at BMC's Center for Infectious Diseases (CID) and are receiving CAB-RPV LA. CID pharmacists and providers will approach all individuals who are actively receiving CAB-RPV LA and assess whether they are interested in participating and ask them to complete the Screening Consent (Appendix C). If individuals are interested in participation, they will be given a warm handoff to study staff. Study staff will meet with patients at CID to complete the enrollment consent form (Appendix D). Participants will also be asked to complete the participant questionnaire at the baseline, midpoint (2-4 months post baseline) and endpoint (at least 6 months post baseline). They will also be asked to complete the Locator Form (Appendix F). Participants will enter the cohort and contribute data to the study from their first CAB-RPV LA injection and be followed in the EHR for a period at least 6 months to determine engagement in care and adherence. Data on clinical endpoints (appointment adherence, viral load, CD4, drug use etc.) will be collected from the EHR.

Cohort 3 Recruitment and Enrollment: EHR data will be used to match patients for Cohort 3 1:1 to patients in Cohort 1 based on the following variables: history of drug use, housing status, sex. Patients in cohort 3 will be a prospective cohort of patients who are HIV positive and not receiving CAB-RPV LA. The Clinical Data Warehouse will match 10 participants to every 1 enrolled in Cohort 1 based on the variables above. CID staff will approach potential participants to assess interest in participation. If individuals are interested in participating, they will be given a warm handoff to the project manager to complete the Enrollment Consent form (Appendix D). They will also be asked to complete the Locator Form (Appendix G). The remainder of their study activity will mirror that of Cohort 2.

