7.3 Data Collection

Objective 2 will include two forms of data collection: 1) participant questionnaires at enrollment (baseline), midpoint (2-4 months), and endpoint (at least 6 months post enrollment) follow-up; 2) clinical and appointment data from the EHR. The baseline questionnaire will be administered to all participants at the time of consenting to participate in the study in order to collect basic sociodemographic characteristics, such as gender identity, education, marital status, income, residence, and other characteristics shown to influence ART outcomes (Mills et al., 2006). The questionnaire will also collect data on potential predictors of intervention success, including unmet needs, satisfaction with care and stigma. (Appendix F). At the midpoint (2-4 months post enrollment) and endpoint (at least 6 months post enrollment), the data will be collected again, using the same data collection instrument. The midpoint data collection and endpoint data collection target dates will be determined by study staff and participants at the first enrollment appointment. For Cohort 1 and Cohort 2 participants, these dates will coincide with their scheduled injections if possible, for convenience.

One week before each target data collection date, study staff will contact the participant using the preferred communication method they specified on their Locator Form at enrollment. Once a data collection date has been determined, study staff will contact participant through their preferred means of communication one day prior to appointment for a reminder.

At the time of data collection, the participant and study staff will meet at determined study location (either Project Trust or CID). Study staff will bring the Participant Folder, Log Book and a ClinCard. The participant will complete the participant survey. If the participant is in Cohort 1 or 2 and is scheduled to receive their

Protocol Title: **CAB-RPV LA Implementation Strategies for High-Risk Populations**

injection at this appointment, the survey can be completed during the 15-minute observation period after the injection.

The clinical and appointment data to be collected from the EHR on all study participants will include clinical endpoints (appointment adherence, viral load, CD4, etc.). Data on clinical endpoints will be collected from their EHR at enrollment at each data collection period using the Chart Review Tool (Appendix E).

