11.0 Statistical Plan

11.1 Study Hypotheses

Objective 2 has the following hypotheses:

- **H1:** Changing the service site will result in $\geq 80\%$ of participants in the community-based intervention arm beginning injections
- **H2:** Of participants in the community-based intervention arm who begin injections, 80% will complete 6 injections
- **H3:** Changing the service site will result in improved engagement in care for participants in the community-based intervention arm compared to matched controls (Cohort 3) at 6 months for intervention patients compared to control group patients
- **H4:** Changing the service site will result in superior HIV viral suppression at 6 months compared to for participants in the community-based intervention arm compared to matched controls (Cohort 3)
- **H5:** Participants in the community-based intervention arm will be equally satisfied with their care compared to patients who receive care in clinic settings (Cohort 2).

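### H4 compares a cohort that must be suppressed at entry with controls who need not be; baseline suppression is not a mandatory model term, and once it is included the 80% power in 11.2 no longer follows

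*Combined protocol and SAP*

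**What the plan says.** Section 5.1 requires Cohort 1 to be "virally suppressed, meaning that their HIV-1 ribonucleic acid is less than 50 copies per mL", and 7.1 repeats it: "Participants must be virally suppressed prior to enrollment". Cohort 3 is described in 5.1 as "Enrolled in care at CID but not receiving CAB-RPV LA", with no viral-load criterion, and 5.2 exempts it in words: "Individuals who are not virally suppressed prior to beginning CAB will be excluded (excluding Cohort 3").

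Section 7.2 matches Cohort 3 to Cohort 1 1:1, "based on the following variables: history of drug use, housing status, sex". Section 5.1 also mentions matching on demographics and further characteristics, but does not name them.

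H4 in 11.1 reads "Changing the service site will result in superior HIV viral suppression at 6 months", Cohort 1 against Cohort 3. Section 11.2 says the study is powered for H4: 20 per cohort, 80% power, alpha 0.05, 90% vs 50%. The 50% is a point-in-time figure for the sites' high-risk patients.

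Section 11.3 plans a multivariable logistic model for H4. It compares baseline clinical attributes between Cohorts 1 and 3, and admits confounders at p ≤ 0.2 or on clinical significance. Baseline viral load should be available, since 7.3 says "Data on clinical endpoints will be collected from their EHR at enrollment". No covariate is named as mandatory.

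**The concern.** The outcome of H4 is the same variable that selects Cohort 1. One cohort starts at 100% on it; the other starts wherever its patients happen to be. A 6-month difference can then reflect who was let in rather than where care was delivered.

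Two things are at stake. If baseline suppression stays out of the model, H4 can be declared a success with no site effect. If it goes in, the bias is largely removed, but unsuppressed controls stop contributing to the cohort contrast, and the control rate used for power is no longer the relevant one. Neither the choice nor its consequence for power is written down.

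**Working it through.** **1. The plan's own figure.** With p1 = 0.90, p2 = 0.50, mean 0.70, two-sided 0.05 (sidedness is not stated; two-sided reproduces the plan):

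n = [1.96·√(2·0.7·0.3) + 0.8416·√(0.09 + 0.25)]² / 0.4² = (1.270 + 0.491)² / 0.16 = 19.4, so 20 per arm.

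Power at n = 20 is 81.3% by this formula and 83.8% by exact enumeration of the uncorrected chi-square test. The figure in 11.2 reproduces.

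**2. If baseline suppression is left out.** The documents do not give the inputs, so these are assumptions. Let π be the share of controls suppressed at entry, s the share of suppressed patients still suppressed at 6 months, and r the share of unsuppressed patients suppressed by then, with s and r equal in both cohorts (no effect). The expected rates are s in Cohort 1 and π·s + (1 − π)·r in Cohort 3. For s = 0.9, r = 0.3, π = 0.5 that is 90% vs 60%.

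Chance of a significant result (either direction, nominal 5%), 20 vs 20, unadjusted, exact enumeration, chi-square / Fisher:

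| s, r | π = 50% | 70% | 80% | 90% |
|---|---|---|---|---|
| 0.9, 0.3 | 62 / 49% | 31 / 20% | 17 / 10% | 8 / 4% |
| 0.8, 0.3 | 41 / 29% | 19 / 12% | 11 / 6% | 7 / 3% |
| 0.9, 0.5 | 36 / 24% | 17 / 10% | 11 / 5% | 6 / 2% |
| 0.8, 0.5 | 19 / 12% | 10 / 6% | 7 / 4% | 6 / 3% |

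The range is 6–62% by chi-square and 2–49% by Fisher. It is small when 90% of controls are suppressed.

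**3. If the p ≤ 0.2 rule is applied to baseline suppression.** Adjust if the screen is passed, otherwise do not; final test chi-square; s = 0.8–0.9, π = 50–90%. Screening against cohort by Fisher gives 4–6% for r = 0.3–0.5 and up to 7.5% at r = 0.1. Screening by chi-square gives 3–5%. Reading the screen as a test against the 6-month outcome also gives 3–5%.

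The screen can still miss the imbalance. With 20/20 vs 17/20 suppressed at entry, Fisher gives p = 0.23 (out). Chi-square is 0.15² / (0.925·0.075·0.1) = 3.24, p = 0.07 (in). Section 11.3 allows either test.

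**4. If baseline suppression is in the model.** Cohort 1 has no unsuppressed members. In a model with cohort and baseline suppression as main effects, unsuppressed controls inform only the baseline term. Example: 18/20 in Cohort 1, 5/10 among suppressed controls. The cohort log-odds ratio is ln(18/2) − ln(5/5) = 2.197, with SE √(1/18 + 1/2 + 1/5 + 1/5) = 0.978. Fitting with or without the unsuppressed controls gives the same two numbers. So the contrast is 20 against m suppressed controls.

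Exact chi-square power, Cohort 1 n = 20:

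| Rates | m = 20 | m = 10 |
|---|---|---|
| 90 vs 50 | 84% | 68% |
| 90 vs 60 | 62% | 47% |
| 90 vs 70 | 36% | 27% |
| 95 vs 80 | 29% | 28% |

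Control rate that gives 80% power with Cohort 1 at 90%:

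| Test | m = 20 | m = 10 |
|---|---|---|
| Chi-square or likelihood-ratio | 52% | 43% |
| Fisher | 47% | 40% |
| Logistic Wald | 42% | not reachable |

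The value m = 10 corresponds to 50% of controls suppressed at entry. At m = 20 the required rate is close to the plan's 50%, so lost sample size is not the difficulty there. The difficulty is that 50% would have to be the rate among people already suppressed.

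**The case against.** The strongest reply is that the plan already handles this. Baseline clinical attributes are compared, viral load is collected at enrollment, and an HIV team would very likely call baseline suppression clinically significant. Step 3 bears this out: under the planned rule the error rate stays near nominal. This stands. A reader might infer that the planned H4 analysis is unadjusted, or biased as written; the documents do not support that. The 6–62% range applies only if the team never puts the variable forward.

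On power, 11.2 is conditional in its wording, its arithmetic is right, and a 50% rate from unselected high-risk patients fits an unselected Cohort 3. A reader might infer a miscalculated sample size; that is not so. But the 50% fits only the unadjusted contrast, the one exposed to entry selection. Ten suppressed controls at 90% and ten unsuppressed at 10% average exactly 50%, with no site effect at all.

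Section 11.2 also notes that counting missing results as detectable lowers control rates. That applies to Cohort 1 too. If 80% of suppressed controls truly stay suppressed, reaching 50% needs 1 − 0.5/0.8 = 37.5% of them to have no 6-month result.

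That this is a pilot is fair, and it favours estimation. Section 11.2 nonetheless claims 80% power, and H4 is worded as superiority.

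**Conclusion.** The concern holds as a gap in prespecification and an unsupported power statement for the powered hypothesis; it should be fixed. Entry suppression is required of Cohort 1, waived for Cohort 3 and absent from the named matching variables, and adjustment for it is permitted but not required.

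The size of any bias depends on s, r and π, none of which the documents give. It is negligible if the term is used, and can be large if it is not and about half the controls are unsuppressed. The power conclusion does not depend on bias occurring: with the term in and Cohort 1 at 90%, 80% power needs suppressed controls at about 43–52%. That range assumes 10 to 20 controls suppressed at entry, main effects only, and a two-sided chi-square or likelihood-ratio test. It is the favourable end, since Fisher and Wald tests need lower rates.

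**What to change.** Choose one route and prespecify it.

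- **Route A, if Cohort 3 enrollment is open:** add HIV-1 RNA below 50 copies/mL, within a window the team sets, to the matching variables in 7.2. A baseline-suppression term then has little or no variation and is not needed.
- **Route B, if enrollment is closed or matching is not feasible:** in 11.3, make baseline suppression a mandatory term in the Cohort 1 vs Cohort 3 model for H4, exempt from the p ≤ 0.2 rule. State the viral-load window and a rule for controls with no result in it. Restricting the contrast to suppressed controls is an alternative, but it breaks the 1:1 matching and the plan should say so. The two are not interchangeable once other covariates enter: in a check with one extra binary covariate, the cohort log-odds ratio was 2.377 with adjustment and 2.424 with restriction.

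Under either route:

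- In 11.1, state that H4 concerns suppression at 6 months among people suppressed at entry.
- In 11.2, keep 60 participants. Replace the 50% control rate and the 80% power with figures for suppressed controls, naming the test and the number of usable controls, as in the power table above. Use the 20-control column only if all 20 are suppressed, as under Route A.
- Report H4 as a pilot estimate with a 95% confidence interval.

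The cost is a few sentences and, under Route A, one more EHR field in a step where "The Clinical Data Warehouse will match 10 participants to every 1 enrolled in Cohort 1". The downside is fewer usable controls or a smaller matching pool, and a less favourable stated power. With 20 per arm, 19/20 vs 16/20 gives a 95% interval of about −7 to +37 points (Newcombe), and 80% power for 95% vs 80% would need about 76 per arm.
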